6.1.1 Waiver of Authorization for Use and Disclosure of Protected Health Information (HIPAA)

A partial waiver of HIPAA is requested for recruitment purposes only. All Protected Health Information (PHI) collected by the study investigator and/or study personnel from patient records JHS and/or UHealth will be destroyed at the earliest opportunity. All Protected Health Inform (PHI) that is acquired from JHS and/or UHealth will not be re-used or disclosed to any other person or entity, except as required by law or for authorized oversight of the research study or for other research for which the use or disclosure of PHI is permissible.

6.2 Payment to Subjects

No payments will be made to subjects as compensation for their participation in this study. The subjects will not be asked to pay for the treatments or participation in study either.

6.3 Informed Consent

6.3.1 Consenting Process

All subjects must provide written consent to participate in this study. An informed consent form (ICF) will be given to each subject. The ICF will contain all United States federally required elements, all International Conference of Harmonization of Technical Requirements for Registration of Pharmaceuticals for Human Use (ICH) required elements, and Health Insurance Portability and Accountability Act Authorization (HIPAA) information in language that is understandable to the subject. The informed consent includes descriptions of all study related procedures, all possible risks to participant, and

the time commitment involved with participating. All consent forms will have IRB approval. The ICF must be understandable to the subject. Translation of ICFs will be done in accordance with local IRB procedures.

Potential participants will be approached by one of the study investigators or research coordinators. Information regarding study participation will be provided to the potential participant prior to consent. Subjects will be given ample time to review the ICF and ask questions before signing. The Investigator or designee and the subject must both sign and date the ICF after review, and before the any study procedures are performed. The subject will receive a copy of the signed and dated form, and the original will be retained in the site study files. The research staff member obtaining consent will document the informed process in the subject's chart for monitoring purposes. The Investigator or his/her designee must emphasize to the subject that study participation is entirely voluntary and that consent regarding study participation may be withdrawn at any time without penalty or loss of benefits to which the subject is otherwise entitled.

6.3.2 Non-English-Speaking Subjects

In addition to English-speaking subjects, Spanish-speakers will also be included in the trial. A certified translated version of the IRB approved English consent form will be made available to non-English speakers. Spanish version questionnaires and other patient-facing materials will also be made available.

6.4 Withdrawal Criteria

All subjects who either screen fails, is withdrawn from the study, or has completed all visits should be de-enrolled from the research database within 2 business days, in accordance with university policies (or respective institutional policy).

Subjects may be withdrawn from the study for any of the following reasons:

- a) A subject does not meet the eligibility criteria (the subject will be considered a screen failure).
- b) A subject withdraws consent.
- c) A subject expires during protocol participation from causes other than the study treatment (not due to adverse events).
- d) At the discretion of the principal investigator for issues of non-compliance, or other behavioral factors.

7. Procedures Involved

15 men with Erectile Dysfunction (ED) of organic origin, that meet all of the inclusion and none of the exclusion criteria, will be enrolled to receive PRP+SWT in an open-label fashion.

Autologous PRP injection + SWT therapy. All subjects in this group will receive 2 sessions of autologous PRP penile injection with 28 ± 2 day treatment interval. 5mL of PRP will be injected at each session. Additionally, patients will receive a total of 3600 shocks over a five-week period, starting at initial PRP injection.

7.1 Schedule of Events:

-

The events table for the conduct of this study is shown below:

Table1:

Schedule of Events		Screening			Follow Up				
Time Point		0-30 days	Week 0	Week 1	Week 2	Week 3	Week 4	Month 3	Month 6
Eve	nt	before randomization	Day 0	Day 7 ± 2	Day 14 ± 2	Day 21 ± 2	Day 28 ± 2	Day 90 ± 14	Day 180 ± 14
Infor	med Consent	x							
Dem	ographics	x							
Medi	cal History	x							
Phys	ical Exam	x							
Dopp	oler Ultrasound	x							X
aires	IIEF	x						X	x
tionna	EDITS							X	x
Ques	VAS		x	x	x	x	x		
Labo	ratory Tests*	x							
EPC	-CFUs	X						X	Х
Brac	hial FMD	X						Х	Х
PRP Injection			х				х		
Shockwave Therapy			Х	Х	Х	Х	Х		
Concomitant Medications/Therapy		x	x	х	х	x	x	x	x
Review Adverse Events			х	x	x	x	х	x	x

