3.1 Primary Endpoints

- Changes in markers of vasodilation (eNOS, nNOS), neo-angiogenesis (VEGF, CD-31), and systemic markers of endothelial function (EPCs, SDF-1α, and SCF).

3.2 Secondary Endpoints (efficacy):

- Differences in Doppler ultrasound parameters (PSV and EDV) from baseline to 6 months post-therapy.
- Treatment satisfaction as assessed by EDITS questionnaire in all subjects.
- Incidence of Serious Adverse Events experienced up to 6 months post-therapy.

3.3 Exploratory Endpoints:

- Change in IIEF-EF score from baseline to 3 and 6 months post-therapy.
- Percentage of subjects that achieve minimal clinically important difference (MCID) in IIEF-EF from baseline to 3 and 6 months post-therapy.
- Percentage of subjects who either decrease or discontinue use of PDE5i after three months post-therapy

4. Study Location

The study will be funded by the CTSI pilot award (GR019191) and coordinated by the University of Miami (UM), Miller School of Medicine, Desai Sethi Urology Institute. All

study visits will take place in the Department of Urology clinics, (PAC: [name], University of Miami Miller School of medicine, Miami, FL. & Lennar: [name]) PRP preparation and SWT therapy administration will take place in the PAC andrology lab and clinic.

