4.1 Additional Study Sites

No additional study sites.

5. Study Population

15 males with ED of organic origin and diabetes. All patients will be regular PDE5i users/responders. Men with ED will be evaluated by IIEF-EF domain and eligible patients will be enrolled in this open label pilot study. Participants who do not meet eligibility criteria will be considered a screen failure and will not receive the study therapy.

5.1 Inclusion criteria:

In order to participate in this study, a patient must:

- 1) Be Male.
- 2) Be 30 to 80 years of age (inclusive).
- 3) Be able to provide written informed consent.
- 4) Have a diagnosis of mild to moderate ED (12-21) or mild ED (22-25) based on IIEF-EF questionnaire score.
- 5) Have diagnosis of Diabetes Mellitus (Type 1 or Type 2) as documented by history of hemoglobin A1C > 7% OR on medical therapy for Diabetes.
- 6) Be in a stable relationship and have a minimum of 2 sexual attempts per month for at least one month prior to enrollment.
- 7) Agree to comply with all study related tests/procedures.

5.2 Exclusion criteria:

In order to participate in this study, a patient must not have any of the following:

- 1) Previous penile surgery of any kind (except circumcision and condyloma removal), such as penile lengthening, penile cancer surgery, penile plication, grafting.
- 2) Previous history of priapism, penile fracture, Peyronie's Disease, or penile curvature that negatively influences sexual activity.
- 3) Abnormal morning serum testosterone level defined as a value lower than 300 ng/dL (±5%).
- 4) Psychogenic ED as determined by study investigator.
- 5) Patients using ICI for management of ED
- 6) Patients with generalized polyneuropathy, neurological conditions, or psychiatric disease (such as bipolar disorder or depression).
- 7) Have a serious comorbid illness or condition that, in the opinion of the investigator, may compromise the safety or compliance of the subject or preclude successful completion of the study.
- 8) History of consistent treatment failure with PDE5 inhibitors for therapy of ED.
- 9) Poorly controlled diabetes as indicated by Hemoglobin a1c > 7.5%.
- 10) Use of antiplatelet medication.

6. Identification and Enrollment of Subjects

6.1 Recruitment and Pre-screening

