- **7.2.13** *Shockwave Therapy (SWT)*: In the treatment group, patients randomized will receive 5 weekly sessions, in which 720 shocks of treatment energy will be applied in every session to each treated region (left and right corpora cavernosa and crura) for a total of 3,600 shocks. Refer to Section 8 for description of Investigational Product (IP) preparation and administration.
- **7.2.14** *Concomitant Medications:* Review of current use of prescription and over the counter (OTC) medications. Participants must discontinue use of PDE5i medications throughout the duration of the study.
- **7.2.15 Review Adverse Events:** Refer to Section 11 for description and reporting of adverse and serious adverse events

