12.1 Data Analysis Plan

Analysis plan: Continuous data will be analyzed using ANOVA with repeated measures, or student's T-Test (where applicable) in order to compare differences between the treatment and control groups. For categorical data, Fisher's Exact test to determine differences between groups. Statistical significance will be evaluated using α =0.05.

13. Risks and Benefits

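### Withdrawal from the study for undefined non-compliance, with no follow-up afterwards and no analysis set, could selectively remove men who are doing poorly

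*Combined protocol and SAP*

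**What the plan says.** Section 6.4 lists the reasons for which a man may be withdrawn from the study. Item (d) reads "At the discretion of the principal investigator for issues of non-compliance, or other behavioral factors". The section defines neither ground and has no separate route for a man who stops study therapy but remains under observation. It adds that screen failures, withdrawn men and completers alike "should be de-enrolled from the research database within 2 business days".

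Section 7.2.14 states: "Participants must discontinue use of PDE5i medications throughout the duration of the study". It attaches no consequence to breaking the ban. Section 5 describes the population: "All patients will be regular PDE5i users/responders". Section 3.3 nevertheless lists as an exploratory endpoint "Percentage of subjects who either decrease or discontinue use of PDE5i after three months post-therapy".

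On analysis, Section 12.1 says "Continuous data will be analyzed using ANOVA with repeated measures", with a t-test as the alternative and Fisher's exact test for categorical data. It gives no analysis population, no denominator for percentages and no rule for missing values. Section 9.1 asks only that missing data be explained. The design is single arm and open label, with 15 men.

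**The concern.** The investigator who decides on a discretionary withdrawal can know how the man is doing. Every man enters with a drug he already responds to, so a man disappointed by the study therapy has the most reason to go back to it. If that is treated as non-compliance and he is withdrawn, his later outcomes are never collected. If the analysis then uses only men with complete data, those remaining are a favourable selection.

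With 15 men and no control arm, a few such losses could change the reading of IIEF-EF change and the MCID percentage, and no comparison group would show it. Endpoints measured late or over a window suffer too, because a man who leaves early is not observed for them.

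**Working it through.** The plan gives no power, effect size, SD or dropout rate, so there is no stated figure to reproduce. The check has three steps.

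**1. What a withdrawn man contributes.** From the schedule in Section 7.1, IIEF and EPC-CFUs are taken at screening, Month 3 and Month 6. Doppler is taken at screening and Month 6 only.

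- Leaves before Month 3: no post-treatment IIEF, EPC-CFU or Doppler value under any method.
- Leaves between Months 3 and 6: Month 3 IIEF and EPC-CFU exist, but there is no Month 6 value and no post-treatment Doppler. A complete-case repeated-measures ANOVA over the three visits discards him entirely. A t-test of Month 3 against baseline, or a mixed model, keeps his Month 3 value.
- Either way, his observation for the Section 3.2 endpoint "Incidence of Serious Adverse Events experienced up to 6 months post-therapy" is cut short.

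A better model therefore repairs only part of the loss. Continued follow-up is needed for the rest.

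**2. Responder rate.** Assume 6 of 15 men truly reach the MCID and that k non-responders are lost. The rate among remaining men is 6/(15 − k); with all treated men as denominator it stays 6/15.

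- k = 0: 6/15 = 40.0%
- k = 1: 6/14 = 42.9%
- k = 2: 6/13 = 46.2%
- k = 3: 6/12 = 50.0%
- k = 4: 6/11 = 54.5%

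**3. Mean change.** Simulation of 40,000 trials of 15 men with no true change, individual changes normal with SD 1, and a two-sided paired t-test at 0.05 on the men remaining. Entries are bias in SDs of change, then type I error.

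| Men lost | The k worst | k at random from the worst 7 | k at random from all 15 |
|---|---|---|---|
| 0 | 0.00; 5.0% | 0.00; 5.0% | 0.00; 5.0% |
| 1 | +0.12; 9.2% | +0.06; 5.1% | about 0; 5.0% |
| 2 | +0.23; 17.5% | +0.12; 6.2% | about 0; 5.1% |
| 3 | +0.33; 29.1% | +0.20; 9.1% | about 0; 5.2% |
| 4 | +0.42; 41.8% | +0.29; 14.3% | about 0; 4.8% |

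The result depends on both the number lost and how closely loss follows outcome. The documents give neither.

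**The case against.** The strongest reply is that the plan does not say any of this will happen, and much of that reply stands.

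- A reader might infer that resuming PDE5i is non-compliance and leads to removal. It is a natural reading of a mandatory ban, but no section says so, and withdrawal is permitted rather than required. The Section 3.3 endpoint points the other way: it makes sense only if men still using PDE5i remain under observation, and concomitant medications are reviewed at Months 3 and 6.
- A reader might infer that the analysis method drops withdrawn men. Complete-case deletion is the usual default of classical repeated-measures ANOVA, not a rule in Section 12.1, and the t-test alternative can keep Month 3 data. The MCID percentage does not go through ANOVA at all; its denominator is simply unstated.
- A reader might infer that de-enrolment deletes the data. The same sentence covers men who finish every visit, so it cannot be read that way.
- A reader might infer that withdrawn men vanish from the SAE count. Section 11.1.2 has all grade 3–5 events entered in the database regardless of association. What can be lost is events after withdrawal.
- A reader might infer bias in the primary result. The primary endpoints are biomarkers, and nothing shows that a man who resumes PDE5i is a failure on those. IIEF-EF change and MCID are exploratory.

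What remains is that the permission to withdraw from the study is written, its grounds are undefined, and nothing provides for follow-up or fixes who is analysed.

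**Conclusion.** The concern holds as a risk, not as a certain bias. Discretionary withdrawal from an open-label study, combined with a complete-case analysis that the plan does not exclude, could remove men who are doing poorly. The effect would fall mainly on exploratory IIEF-EF change and the MCID percentage. Doppler, Month 6 EPC-CFU and the SAE window lose information without any clear direction of bias.

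Under the assumption of 6 true responders and losses confined to non-responders, 1 to 4 losses inflate the MCID rate by about 3 to 15 percentage points. For mean change with no true effect, one or two losses drawn at random from the worst seven men barely move type I error (5.1% and 6.2%); losing the three worst raises it to 29.1%. If loss is unrelated to outcome, bias is about zero and only precision suffers. The change is worth making because it is cheap and the sample is small.

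Separately, the ban in Section 7.2.14 and the endpoint in Section 3.3 contradict each other. Until they are reconciled, the handling of data after PDE5i resumption has no clear basis.

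**What to change.** **Section 6.4.** Separate stopping study therapy from leaving the study. Continue to collect Month 3 and Month 6 outcomes and adverse events on every treated man unless he withdraws consent.

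**Section 12.1.**
- Define the analysis set as all treated men, and use a mixed model that keeps incomplete cases.
- Use all treated men as the MCID denominator, counting a missing Month 6 value or PDE5i resumption as non-response.
- Flag IIEF scores taken after PDE5i resumption. These men are known PDE5i responders, so a mixed model on every visit would otherwise credit the drug's effect to study therapy. Add one sensitivity analysis that does not credit those scores (for example, set to baseline) and one using observed values.

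**Sections 7.2.14 and 3.3.** Reconcile the PDE5i ban with the endpoint on decreasing or discontinuing PDE5i, and align the resumption rule above with the outcome. Which passage should change is for the clinical team.

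The cost is wording, some extra contact with men who stopped therapy, and possibly a less favourable responder rate.

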7.2 Description of Study Procedures

- **7.2.1** *Informed Consent:* Refer to Section 6.3 for details regarding the informed consent process. Study procedures will be completed only after participants have signed the informed consent documentation.
- **7.2.2** *Demographics:* Demographic characteristics will be recorded including: date of birth, gender, marital status, race and ethnicity.
- **7.2.3** *Medical History:* Assessment of current and past medical, surgical, and social history will be conducted.
- **7.2.4** *Physical Examination:* Genitourinary/Reproductive system physical exam will be performed.
- **7.2.5 Doppler Ultrasound:** Penile Doppler ultrasound will be performed as standard of care for the management of erectile dysfunction. Results from within the past 12 months can be extracted from the medical record for use in this study.
- **7.2.6** *International Index of Erectile Function (IIEF) Questionnaire*: This validated 15-item self-evaluation scale provides pre and post treatment clinic evaluations of erectile function, orgasmic function, sexual desire, satisfaction in sexual intercourse and general satisfaction. If the subject has completed the IIEF questionnaire within the past 6 months, those results may be requested and used for the purpose of this research study. Questionnaires will be completed prior to therapy at injection visits.
- 7.2.7 Erectile Dysfunction Inventory of Treatment Satisfaction (EDITS) Questionnaire: This is a psychometrically sound questionnaire used to assess satisfaction with medical treatment modalities for erectile dysfunction.
- **7.2.8** *Visual Analogue Pain Scale (VAS)*: The visual analog scale (VAS) is a validated, subjective measure for acute and chronic pain. Scores are recorded by making a handwritten mark on a line that represents a continuum between "no pain" and "worst pain".
- **7.2.9** *Laboratory Testing:* Hematology, chemistry, hemoglobin A1C, and serum testosterone lab test results will be collected at screening. If any standard of care labs testing has been performed within 12 months of the date of the screening visit, those results may be used for the purpose of this study.
- 7.2.10 Endothelial Progenitor Cell Colony Forming Units (EPC-CFUs): Peripheral blood samples will be collected from participants for isolation of EPCs using Ficoll-Paque density gradient. Plasma will be aliquoted and stored for future analysis. Five million cells will be seeded on 6-well Fibronectin-coated dishes (BD Biosciences) in CFU-Hill medium (Stem Cell Technologies, cat#05900)4 and incubated at 37°C in humidified 5% CO2. Non-adherent cells will be collected after 48 hours, and 1 million cells will be seeded on 24-well Fibronectin-coated dishes. On day 5, EPC-CFUs will be counted in 6 wells and the average will be obtained.
- **7.2.11** Brachial Artery Flow Mediated Dilation (FMD): FMD% is a non-clinical measure; it is a tool used specifically for research to obtain an understanding the functionality of the vascular endothelium. 2D ultrasound will be used to measure Flow Mediated

Diameter percent change (FMD%). All measurements of the brachial artery diameter and FMD% will be performed in the morning, in a quiet and dark room and at controlled ambient temperature. Subjects will fast overnight and refrain from consuming caffeine, nicotine, or other stimulants for at least 8 hours prior to ultrasound and should refrain from vigorous exercise for at least 4 hours prior to ultrasound. Subjects are permitted to drink water and take medications (except PDE5 inhibitors) as usual. The subject will rest for 10 minutes in the supine position prior to scan. The subject's right arm will be comfortably immobilized in an extending position, allowing for ultrasound scanning of the brachial artery 5–10 cm above the antecubital fossa. In each examination, recording of vessel images will be followed by inflation of a cuff to supra-systolic pressure (40 to 50 mmHg above systolic pressure) for 5 minutes. Then the cuff will be deflated, and the brachial artery diameter will be imaged and recorded for 3 minutes.

- **7.2.12** *Platelet-Rich Plasma (PRP) Injection*: Approximately 120mL of blood will be collected from participants for preparation of investigational product. Refer to Section 8 for description of Investigational Product (IP) preparation and administration.
- **7.2.13** *Shockwave Therapy (SWT)*: In the treatment group, patients randomized will receive 5 weekly sessions, in which 720 shocks of treatment energy will be applied in every session to each treated region (left and right corpora cavernosa and crura) for a total of 3,600 shocks. Refer to Section 8 for description of Investigational Product (IP) preparation and administration.
- **7.2.14** *Concomitant Medications:* Review of current use of prescription and over the counter (OTC) medications. Participants must discontinue use of PDE5i medications throughout the duration of the study.
- **7.2.15 Review Adverse Events:** Refer to Section 11 for description and reporting of adverse and serious adverse events

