7.3 Description of Study Visits

7.3.1 Screening Visit

Visit 1 (0 – 28 days before therapy): The basic work-up will take place, including medical and sexual history, as well as necessary lab tests (testosterone, prolactin, hematology, chemistry), if not available during the last 12 months prior to screening. Subjects will complete the IIEF questionnaire. We will ensure that patients have 4 attempts for intercourse Screening visit can occur on same day as first injection + SWT. Refer to table 1 for procedures to be performed at the Screening visit.

7.3.2 Treatment Visits: Week 0 – Week 4

Upon evaluation of eligibility, subjects will be randomized to one of the two parallel study groups using an online program, and initiate treatment on the same day.

There will be 5 treatment visits for all groups, each occurring at weekly intervals (\pm 2 days), for a total duration of five weeks. Subjects will complete a Visual Analogue Scale (VAS) pain score after the end of each treatment. Refer to table 1 for all procedures to be performed at the treatment visits.

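### The protocol's PDE5i ban decides the PDE5i-reduction endpoint, and no minimum time off PDE5i is guaranteed before the baseline IIEF in a single-arm trial

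*Combined protocol and SAP*

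**What the plan says.** The synopsis describes a single-arm, open-label pilot in 15 men. On PDE5i use at entry, section 5 says: "All patients will be regular PDE5i users/responders". On use during the trial, section 7.2.14 says: "Participants must discontinue use of PDE5i medications throughout the duration of the study". The synopsis gives the duration as 7 months and counts one month of screening within it.

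Section 3.3 lists three exploratory endpoints: change in IIEF-EF to 3 and 6 months, the share of men reaching the MCID on IIEF-EF, and the share who cut down or stop PDE5i beyond three months after therapy.

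The baseline IIEF is described in several places:
- Section 7.2.6: "If the subject has completed the IIEF questionnaire within the past 6 months, those results may be requested and used". The same section also has questionnaires filled in before therapy at injection visits.
- Section 7.3.1, for the screening visit: "Subjects will complete the IIEF questionnaire". It then adds "We will ensure that patients have 4 attempts for intercourse" and lets screening take place on the day of the first injection and shockwave session.
- Table 1 (section 7.1) marks the IIEF at screening, Month 3 and Month 6 only.
- Inclusion criterion 4 (section 5.1): "Have a diagnosis of mild to moderate ED (12-21) or mild ED (22-25) based on IIEF-EF questionnaire score".

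None of these says whether the score is to be taken on or off PDE5i. The one measurement with a PDE5i hold attached is brachial FMD (7.2.11).

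**The concern.** Without a control arm, a man's own baseline is his only comparator, so anything else that changes between baseline and follow-up is counted as therapy effect. PDE5i status can change, because the protocol itself orders men to stop a drug that section 5 says they use and respond to. If the baseline IIEF reflects erections with the drug and the follow-up IIEF reflects erections without it, the difference mixes two effects that cannot be separated afterwards.

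The PDE5i-reduction endpoint has a more direct problem. It is meant to show that men need the drug less, but it is assessed while the protocol forbids the drug.

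The secondary objective in the synopsis names the IIEF as its measure of efficacy. Although section 3.3 ranks the IIEF endpoints as exploratory, they are likely to be read as the pilot's clinical signal.

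**Working it through.** The plan gives no effect size, SD, MCID value or power figure for the IIEF, so there is no stated figure to reproduce. The check is mainly a comparison of the text.

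**PDE5i-reduction endpoint.** Assume reduction is judged against use at entry, which the protocol does not state.
- Inputs: N = 15 (section 5); PDE5i forbidden throughout (7.2.14); assessment beyond three months after therapy (3.3); follow-up of 6 months inside the stated duration (synopsis). The assessment therefore falls within the ban.
- Let u be the number of men using PDE5i at entry. Under full compliance all u have stopped, so the result is u/15.
- With u = 15, as section 5 describes, the result is 15/15 = 100%. The exact 95% lower limit is 0.025^(1/15) = 0.782, so the report would read 100% (78.2% to 100%). It would look like a strong finding, yet no therapy effect enters the calculation.
- If all are users and those who do not comply make no reduction, 90% or 80% compliance gives an expected 90% or 80%.
- If u is below 15, the result is below 100% even with full compliance. For example, an assumed u = 12 gives 12/15 = 80%.

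In each case the result depends on entry use and adherence.

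**Time off drug before the baseline IIEF.** Each permitted source of the score compares with the ban as follows:

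| Source of score | Off-drug time guaranteed |
|---|---|
| Historical score, up to 6 months old (7.2.6) | None; it can predate consent and so the ban |
| Screening visit on the day of first treatment (7.3.1) | None; the gap can be 0 days |
| Screening visit earlier in the window (0-28 days in 7.3.1, 0-30 in Table 1) | None stated; the ban may begin at that same visit |
| Before therapy at an injection visit (7.2.6) | None stated; Table 1 marks no IIEF at Week 0 or Week 4 |

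The rule on 4 intercourse attempts gives neither a period nor a drug condition, so it does not create an off-drug run-in.

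**Effect on IIEF-EF change.** Let T be the mean true change from therapy, w the mean points lost by going from on drug to off drug, and f the share of men with an on-drug baseline and off-drug follow-up. Then:

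expected observed mean change = T − f·w

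The documents give none of T, w or f. To show the mechanism only, assume T = 5 and f = 1. An assumed w of 2, 4 or 6 gives 5 − 2 = +3, 5 − 4 = +1 or 5 − 6 = −1. With f = 0 the observed change is +5. The direction is probably downward, because section 5 describes responders and exclusion criterion 8 removes consistent PDE5i failures.

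**The case against.** Several points on the other side have force.

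- **The ban may start before Day 0.** The stated 7 months include screening, so on a literal reading men stop the drug at screening. It would go too far to say the protocol has no off-drug time. But no minimum is set, the IIEF belongs to the screening visit itself, and that visit may be the treatment day.
- **A fresh IIEF is already scheduled.** In 7.3.1 the allowance for existing results attaches to the laboratory tests; the IIEF sentence is unconditional, and Table 1 agrees. Section 6.1 describes pre-screening from records using IIEF-EF, an obvious use for an old score. A reader might infer that the sponsor plans to use old scores as baseline. The documents do not support that; they only fail to limit reuse to pre-screening.
- **15/15 is conditional.** Regular PDE5i use appears in the description of the population, not among the seven inclusion criteria. A non-user could enrol and could not reduce. The conflict between ban and endpoint remains, but the figure needs all 15 to be users.
- **Medication use is reviewed.** Section 7.2.14 provides for "Review of current use of prescription and over the counter (OTC) medications", and the Table 1 row "Concomitant Medications/Therapy" is marked at screening, every treatment visit, Month 3 and Month 6. This would show who changed status between visit IIEFs. It does not cover a historical score, and within a man who changed status it cannot separate withdrawal from therapy.
- **The stakes are limited.** All three affected endpoints are exploratory, in a 15-man pilot with a biomarker primary endpoint. This stands.

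**Conclusion.** The point holds in two parts. The conflict between 7.2.14 and the PDE5i-reduction endpoint follows from the text: among compliant men using PDE5i at entry the success rate is 100%, or 15/15 if section 5 describes everyone enrolled and reduction is counted from entry. The endpoint cannot show reduced need for the drug.

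The IIEF part is a permitted confounding rather than a certain one. On-drug baselines can be compared with off-drug follow-up because no minimum off-drug period is guaranteed and the baseline score is not pinned down. The size cannot be estimated from the documents, and none is claimed.

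A reader might infer that this threatens a false claim of efficacy. The likely direction is the opposite: a real benefit could be understated. A reader might also infer that the primary endpoint is compromised; the IIEF reuse rule does not bear on the biomarkers.

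**What to change.** 1. **PDE5i endpoint (3.3, 7.2.14).** Either drop it and keep the ban to Month 6, so that follow-up IIEFs in compliant men are off drug, or permit PDE5i again after a stated time and record use and last dose at each IIEF. The second option keeps the endpoint, but later IIEF scores may then be on drug against an off-drug baseline, so the analysis must take status into account.
2. **Baseline (7.2.6, 7.3.1, Table 1).** Define baseline as a fresh IIEF completed before first treatment and after a stated minimum period off PDE5i within the existing screening window. The length is for the sponsor to choose. If the period starts at consent, the window limits it to 28 days (7.3.1) or 30 days (Table 1), and these should be aligned. Use historical scores for pre-screening only. Allow same-day screening and treatment only for men already off drug for that period.
3. **Criterion 4 (5.1).** State whether the 12-25 range applies to the pre-screening score or to the off-drug baseline.

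The cost is more than wording. Same-day enrolment becomes less common, men may spend some weeks off PDE5i before treatment, which needs consent text, and recruitment of 15 may slow. If the period starts at consent, the IIEF moves towards Day 0, where Table 1 has no mark. If criterion 4 is applied to the off-drug score, a man could fail screening after completing the work-up and the time off drug. One exploratory endpoint is lost or redefined. Last-dose timing is a new data item only under the second option in item 1.
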